#### R code and sample output for primary outcome with Seemingly Unrelated Regression model using systemfit

```
> fit12=systemfit(list(Eq1 = log_mi ~ Treatment + log_mi_base,
                      Eq2 = log_cpeptide_steady ~ Treatment +
                          log_cpeptide_steady_base),
                  method='SUR',
                  data=RISEM15)

> linearHypothesis(fit12, test = "Chisq",
                  c('Eq1_TreatmentTreat2=0', 'Eq2_TreatmentTreat2=0'))
```

Hypothesis: Eq1\_TreatmentTreat2 = 0      Eq2\_TreatmentTreat2 = 0

Model 1: restricted model

Model 2: fit12

	Res.Df	Df	Chisq	Pr(>Chisq)
1	xxx			
2	xxx-2	2	xxxx	x.xxx ← pvalue for the 2-DF joint statistical test of both sensitivity and secretion variables of the treatment arm difference

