During analysis of the baseline data, we found that the DI (i.e. sensitivity x secretion) is sometimes paradoxically lower in pediatric participants than adult participants, despite the fact that the insulin sensitivity vs. C-peptide curves describing the relationship between these two variables appears higher in children. This contradictory finding is at least in part due to the fact that the range of values for insulin sensitivity among children is narrow compared to that of adults, i.e., children are more insulin resistant than adults. Further, the log-log slopes of insulin sensitivity vs. C-peptide responses are not equal to -1 in children or adults (or overall). Although the untransformed data show a clear inverse relationship typical of a hyperbolic curve, the slopes for each of the primary outcome measures on the log scale is approximately -0.3 (not -1.0 as may have been expected); this is a hyperbola but not a square hyperbola. Thus, the approach of performing the primary outcome analysis comparing treatment groups after washout, with a test of difference in DI at Month 15 adjusted for baseline, may not be appropriate and needed to be reassessed.

Several options were considered including a simple linear regression model (on a log scale) of C-peptide (and insulin) release as a function of insulin sensitivity, with a term for treatment group and adjusting for both variables at baseline. However, this was also deemed inappropriate because that model would estimate the difference in C-peptide (and insulin) release between groups assuming that there was no difference in insulin sensitivity between groups. Rather, we want to account for movement of both variables simultaneously without forcing a specific relationship between them. This can be accomplished by performing the primary outcome analysis using two separate models: insulin sensitivity at Month 15 vs. treatment arm (adjusted for baseline) and C-peptide (and insulin) release at Month 15 vs. treatment arm (adjusted for baseline), where the two models are fit simultaneously using Seemingly Unrelated Regression techniques. This provides an

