estimate of the treatment group difference in insulin sensitivity as well as the treatment group difference in the release of the beta-cell peptides, while allowing for the correlation among the insulin sensitivity and peptide release measures. This yields an estimate of the joint covariance structure of the two models, and allows a joint statistical test of both variables using a 2-DF chi-square test of the treatment arm difference in each model. Thus, we will be able to test whether both the insulin sensitivity and C-peptide (and insulin) release variables are different across treatment groups at Month 15, adjusted for their baseline value.

This approach will provide a clear answer to the question of whether the Month 15 result differs by treatment, adjusting for baseline measures. However, given that an underlying reciprocal relationship is expected, it is possible that a significant difference could be found between groups, but that this represents a proportional shift without a specific improvement in peptide release adjusted for sensitivity. In other words, the data points could lie on a different part of a shared relationship curve such that the change represents a mutually compensated change in these terms without a separate underlying change in beta-cell function. Therefore, if the results of the two-model analysis are significant, further analysis will evaluate the patterns of change in either or both variables within each group.

Below is sample Primary Outcome R code for this primary analysis.

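### Each primary equation adjusts only for its own baseline. Adding the other baseline to both is a cheap, optional safeguard against arm-specific dropout and some loss of precision.

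*SAP*

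**What the plan says.** The narrative part of the SAP (under the approval heading) and its R code section agree on the covariates.

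- Insulin sensitivity: "Eq1 = log_mi ~ Treatment + log_mi_base".
- C-peptide: "Eq2 = log_cpeptide_steady ~ Treatment", followed on the next code line by baseline steady-state C-peptide and nothing else.
- Text: the aim is to test whether the two variables are "different across treatment groups at Month 15, adjusted for their baseline value".
- Primary test: a "2-DF chi-square test of the treatment arm difference in each model".

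The narrative also describes a single-equation model of release on sensitivity, "with a term for treatment group and adjusting for both variables at baseline". It rejects that model because the release difference would be estimated as if sensitivity did not differ between groups. That is an objection to conditioning on Month 15 sensitivity. Nothing is said against using both baselines. The narrative further reports that "the slopes for each of the primary outcome measures on the log scale is approximately -0.3", so the two quantities are related at baseline.

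**The concern.** Leaving the other baseline out of an equation fixes its coefficient at zero. The SAP says it wants to avoid forcing a particular relationship between sensitivity and release, yet this is a restriction of that kind and it is not argued for.

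Two things could follow. If the other baseline predicts the outcome beyond the own baseline, residual variance that could be removed is left in. If participants without a Month 15 clamp contribute nothing and their absence depends on the omitted baseline differently by arm, those who remain differ between arms on a predictor that the model ignores. Part of that imbalance would then appear as a treatment effect. SUR also uses the zero restrictions to link the equations, so a wrong restriction in one can disturb the treatment estimate in the other.

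**Working it through.** **No figure to reproduce.** The SAP gives no sample size, SD, dropout rate or power. All sizes below rest on assumed inputs; only the covariate lists, the 2-DF test and the slope of about -0.3 come from the SAP.

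**When is the cross-baseline coefficient zero?** On the log scale, write C = -0.3·S + B, with S sensitivity and B a beta-cell component. Let S persist to Month 15 with factor a, and B with factor b. Then

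E(C15) = -0.3·a·S0 + b·B0 = -0.3·a·S0 + b·(C0 + 0.3·S0) = b·C0 + 0.3·(b − a)·S0.

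The coefficient of baseline sensitivity is 0.3·(b − a). For a/b = 0.6/0.9 it is 0.3 × 0.3 = 0.09; for 0.4/0.9 it is 0.3 × 0.5 = 0.15; for a = b it is 0. Clamp measurement error adds further cross-terms. The SAP does not give a or b.

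**Simulation A: persistence model.** Assumed: 45 per arm; about 20% missing (about 71 of 90 left); dropout logistic in baseline M/I in one arm (coefficient 1.5) and constant at 17.5% in the other; no true effect. C-peptide is -0.3·M/I + 0.35·B, rescaled to SD 1, with noise SD 0.3 (M/I) and 0.2 (C-peptide). There were 4,000 replicates per setting.

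| a/b | Absolute bias, own baseline (M/I, C-peptide) | Absolute bias, both baselines |
|---|---|---|
| 0.6/0.9 | 0.025, 0.029 SD | at most 0.001 |
| 0.4/0.9 | 0.051, 0.057 SD | at most 0.001 |

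The two biases have opposite signs. The empirical SD of the C-peptide effect in the second row is 0.184, so the larger bias is 0.057/0.184 ≈ 0.31 of a standard error.

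Power of the 2-DF test with no dropout and a beta-cell effect of 0.45 latent SD, own baseline then both baselines:
- 0.6/0.9: 84.0% to 85.1%
- 0.4/0.9: 80.2% to 85.7%
- 0.9/0.6: 54.4% to 56.9%
- equal persistence: 63.4% to 63.3%

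**How SUR carries the bias.** One sample of 600,000 at 0.4/0.9, with the same kind of dropout:
- M/I equation alone by OLS, own baseline: -0.002 SD.
- SUR as coded: +0.043 (M/I) and -0.047 (C-peptide).
- Both baselines in both equations: -0.002 and 0.001.

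So the M/I bias comes from the joint fit. The signs depend on which arm has the selective dropout.

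**Simulation B: cross-lag set directly.** Cross-lag means the slope of an outcome on the other baseline, given its own. Assumed: own-baseline slope 0.6, residual correlation -0.3, baseline correlation -0.3, dropout driven by baseline C-peptide. Absolute bias in the M/I effect, own-baseline model:

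| Dropout pattern | Cross-lag -0.1 | Cross-lag -0.2 |
|---|---|---|
| Same in both arms (11%) | within 0.006 | within 0.006 |
| One arm only (12%) | 0.01 | 0.02 |
| Opposite directions by arm (11%) | 0.02 | 0.04 |
| Opposite directions, heavy (22%) | 0.03 | 0.07 |

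With cross-lag 0 there was no bias under any pattern. With both baselines the bias was at most about 0.006 SD throughout. The standard error with dropout, at 90 randomised, was about 0.17 to 0.19 SD. In the heaviest setting the type I error of the joint test was 0.069 with own baselines and 0.059 with both.

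Power (11% dropout, true effects 0.4 and 0.3 SD), own baseline then both:
- cross-lag 0: 85.2% to 84.7%
- -0.1: 86.4% to 87.0%
- -0.2: 87.6% to 90.2%
- -0.3: 88.7% to 94.8%

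The standard error changed by about +1%, 0% and -3% for cross-lags 0, -0.1 and -0.2.

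**Further run on the persistence model.** Selective dropout in one arm with unequal persistence gave 0.02 to 0.045 SD. Equal persistence gave at most 0.007 SD, the same pattern in both arms gave no bias, and the power gain was 0 to 4 points.

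**The case against.** The strongest reply is that own-baseline covariate adjustment is a standard, valid randomised comparison, that text and code state it consistently, and that differing regressors are what let SUR improve on OLS. With both baselines in both equations, SUR point estimates reduce to OLS. All of this stands. The efficiency given up is small, however: about 1% in standard error and up to half a point of power when the cross-lag is truly zero.

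Four stronger readings are tempting, and the SAP does not support them.

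- **Withdrawal related to the other baseline is enough to bias the comparison.** It is not. The cross-lag must be non-zero and the dropout pattern must differ by arm. The SAP shows neither.
- **The reported slope makes a zero cross-lag implausible.** The value "approximately -0.3 (not -1.0 as may have been expected") is a cross-sectional baseline relation. It says nothing about relative persistence to Month 15.
- **The plan discards non-completers and wastes their data.** Use of completers only is inferred from the data set name RISEM15 and from a model with one Month 15 response per equation, in code offered as a sample. Missing-data rules may be in the protocol, which is not at hand. Participants with no Month 15 value would add almost nothing to a single-follow-up comparison through their baseline alone, and the change proposed here is itself a complete-case fit.
- **The second baseline was dropped by oversight.** The SAP gives no reason for the choice, so intent cannot be inferred.

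**Conclusion.** The point holds in conditional form. The primary equations impose zero cross-baseline coefficients without justification. If those coefficients are not zero, precision is lost; if missingness also depends on the omitted baseline differently by arm, the treatment estimates are biased, possibly in both equations.

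The size is modest. With 90 randomised and about 20% missing, bias is about 0.02 to 0.06 SD (0.07 in the most extreme pattern tried), against a standard error of about 0.15 to 0.24 SD across the runs. Power changes from half a point lost to about 6 points gained, and type I error moves little. Sample size, dropout, persistence, noise and effect sizes are all assumptions.

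This is a cheap, optional improvement. The present model is not invalid.

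**What to change.** Add `log_cpeptide_steady_base` to Eq1 and `log_mi_base` to Eq2, so that both equations contain treatment and the same two baselines. Do likewise for the maximal C-peptide and insulin release measures, using the matching release baseline. Keep the joint 2-DF test of the two treatment coefficients. In the narrative, replace the own-baseline wording with adjustment of each outcome for baseline sensitivity and baseline release.

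This does not condition on Month 15 sensitivity, so the SAP's reason for rejecting the single-equation model does not apply. A complete-case fit would then need only that Month 15 data are missing at random given arm and both baselines; the plan should state that assumption or point to where it is stated.

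Cost: one covariate per equation, one phrase of text, no new data, one residual degree of freedom per equation, and the small efficiency loss noted above if the cross-lag is zero.
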